Subjects enrolled in the study must require daily doses of calcium supplements of  $\geq 1000$ mg prior to baseline (Day 1). Subjects enrolled in the study must also require minimum daily doses of active vitamin D (1,25[OH]2D3 [1,25-dihydroxycholecalciferol, (eg, calcitriol,  $\alpha$ -calcidol [1(OH)D3]]) of  $\geq 0.25$ µg calcitriol or equivalent. Subjects will be expected to adhere to standard meals provided during their confinement in the CRC during each period (from check-in on Day -2 until discharge on Day 2). All subjects (in all treatment arms) will take their usual doses at the usual regimen of supplemental oral calcium and active vitamin D on Day -2 and Day-1. For all subjects in all cohorts, active vitamin D supplements must be withheld on Day 1 through the completion of all study procedures on Day 2. Subjects may then resume active vitamin D following final study procedures on Day 2 at the discretion or direction of the investigator.

During Treatments A, B, and C (Cohorts 1 and 2), supplemental oral calcium and active vitamin D will be withheld starting on Day 1 (predose), through the completion of all study procedures on Day 2 for both the once-daily and twice-daily dosing regimens. Upon completion of all study procedures on Day 2, subjects will then resume their usual supplemental oral calcium and active vitamin D at their next usual daily schedule.

During Treatments D, E, and F (Cohorts 3 and 4), subjects will withhold active vitamin D on Day 1 but take their usual dose(s) of supplemental oral calcium according to their usual regimen, regardless of the schedule/timing of IP administration(s). Critically, oral calcium supplementation should be identical on Day-1, Day 1 and Day 2 in Treatment Period 1 and Treatment Period 2. On Day 2, subjects will continue with their usual supplemental calcium regimen (ie, identical on Day -1 and Day 1) and, following the completion of all study procedures, subjects will then re-start their active vitamin D at their next usual daily schedule.

During the crossover washout period, subjects will be instructed to take their usual doses of supplemental oral calcium and active vitamin D.

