**Table 1 Schedule of Assessments**

Study Visit	Screening		Predose Assessment		Treatment Period 1		Washout	Predose Assessment		Treatment Period 2		Follow-up
	Admin.	Clinical	TP1, D-2	TP1, D-1	TP1, D1	TP1, D2	W a,b	TP2, D-2	TP2, D-1	TP2, D1	TP2, D2	FU
Study Relative Day/ Study Procedures	-120 to -03	-28 to -03	-2	-1	1	2		-2	-1	1	2	Follow-up c
Withhold supplemental oral calcium and active vitamin D s					X t					X t		
Administration of supplemental oral calcium only (no active vitamin D) u					X v					X v		

HBsAg=hepatitis B surface antigen; HCV=hepatitis C virus; HIV=human immunodeficiency virus

a Washout period should be  $\geq 5$  days (ie, 120 hours) and  $\leq 30$  days between first dose of each treatment period (whether dosing regimen is BID or QD).

b The investigator may elect to keep the subject in-clinic for the duration of the study, if the washout period is short (eg, 120-172 hours) and/or there are any safety concerns, and provided that there is a minimum washout of  $\geq 120$  hours between administration of IP in each treatment period.

c A follow-up visit must be completed  $30 \pm 2$  days after the last dose of IP.

d If applicable.

e Review and update medical history and re-confirm eligibility.

f In the event a subject is prematurely discontinued from the study, every attempt should be made to complete these assessments.

g The safety blood and urine assessments (Period 1 and Period 2), pregnancy test (for all females, Period 2), physical exam (Period 2), and weight (Period 2) should be collected after the scheduled serial PK and PD assessments have been completed on this study day, and prior to discharging the subject from the Clinical Research Center.

h Randomization will occur prior to administration of IP at Treatment Period 1, Day 1 only after all eligibility criteria have been confirmed/re-confirmed.

i Vital sign measurements should be collected in the supine position at each time point.

j See Table 2, Table 3, and Table 4 for detailed collection time points.

k Weight measurement only.

l ECGs will be performed in triplicate measurement at each time point.

m Includes thyroid function tests, and estimated creatinine clearance (Cockcroft–Gault formula) at Clinical screening visit only.

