**Table 1 Schedule of Assessments**

Study Visit	Screening		Predose Assessment		Treatment Period 1		Washout	Predose Assessment		Treatment Period 2		Follow-up
	Admin.	Clinical	TP1, D-2	TP1, D-1	TP1, D1	TP1, D2	W a,b	TP2, D-2	TP2, D-1	TP2, D1	TP2, D2	FU
Study Relative Day/ Study Procedures	-120 to -03	-28 to -03	-2	-1	1	2		-2	-1	1	2	Follow-up c

†Supplemental oral calcium and active vitamin D will be withheld starting on day of dosing, and through the end of Day 1. Subjects will then resume their usual supplemental oral calcium and active vitamin D at their next usual daily schedule on Day 2.

‡Applies to subjects assigned to Treatment D, Treatment E and Treatment F only.

¶Supplemental oral calcium should be taken according to the subject's usual daily regimen (but active vitamin D must be withheld).

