On Day 1 of Treatment Period 2, subjects will receive the alternative treatment (according to the randomization schedule), following a washout period ( $\geq 5$  days [ie, 120 hours] and  $\leq 30$  days) between administration of the dose or first dose ([for once-daily or twice-daily dosing, respectively] of each treatment period). All investigational product will be administered via SC injection into alternating thighs at each administration.

At each treatment period, subjects will report to the CRC on Day-2, remain in the CRC through Day 2, and be discharged following the last scheduled assessment on Day 2 (investigators may elect, at their discretion, to keep the subject in-clinic after Treatment Period 1 for the duration of the washout period, eg, if the washout period is short [eg, 120-172 hours] or there are any safety concerns).

For once-daily treatments (Treatments B and E), subjects will receive a single subcutaneous dose of rhPTH(1-84) in the morning on Day 1. For twice-daily treatments (Treatments A, C, D, and F), subjects will receive a subcutaneous dose of rhPTH(1-84) in the morning followed by the second dose 12 hours later on Day 1 (in the opposite thigh). If randomized to rhPTH(1-84) with calcium, subjects will take their usual supplemental oral calcium on Day 1 per their usual schedule. Prior to discharge from the CRC at each treatment period, subjects will be given specific instructions for when to take their supplemental oral calcium and active vitamin D supplements during the day(s) when subjects are not in the CRC.

Subjects enrolled in the study must require daily doses of calcium supplements of  $\geq 1000$  mg prior to baseline (Day 1). Subjects enrolled in the study must also require minimum daily doses of active vitamin D of  $\geq 0.25\mu\text{g}$  (ie,  $0.25\mu\text{g}$  calcitriol or equivalent). Subjects will be expected to adhere to standard meals provided during their confinement in the CRC during each period (from check-in on Day -2 until discharge on Day 2). All subjects (in all treatments) will take their usual doses at the usual regimen of supplemental oral calcium and active vitamin D on Day -2 and Day -1. For all subjects in all cohorts, active vitamin D supplements must be withheld on Day 1 through completion of all study procedures on Day 2. Subjects may resume active vitamin D following final procedures on Day 2 at the discretion or direction of the investigator.

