During Treatments A, B, and C (Cohorts 1 and 2), supplemental oral calcium and active vitamin D will be withheld starting on Day 1 (predose), through the completion of all study procedures on Day 2 for both the once-daily and twice-daily dosing regimens. Upon completion of all study procedures on Day 2, subjects will then resume their usual supplemental oral calcium and active vitamin D at their next usual daily schedule.

During Treatments D, E, and F (Cohorts 3 and 4), subjects will withhold active vitamin D on Day 1 but take their usual dose(s) of supplemental oral calcium according to their usual regimen, regardless of the schedule/timing of investigational product administration(s).

Critically, oral calcium supplementation should be identical on Day -1, Day 1 and Day 2 in Treatment Period 1 and Treatment Period 2. On Day 2, subjects will continue with their usual supplemental calcium regimen (ie, identical on Day -1 and Day 1), and, following the completion of all study procedures, subjects will then re-start their active vitamin D at their next usual daily schedule.

During the washout period, subjects will be instructed to take their usual doses of supplemental oral calcium and active vitamin D.

Any subject who experiences symptoms of hypocalcemia or hypercalcemia may be treated at the investigator's discretion, as per local standards. This may include, but is not limited to, intravenous (IV) calcium and/or fluids.

For all dosing regimens, rhPTH(1-84) will be administered in the morning of Day 1 of each treatment period following an overnight fast of at least 8 hours. Subjects will continue to fast until approximately 2 hours after rhPTH(1-84) administration, at which time a standardized meal will be served (see Section 4.3 item 5). For subjects assigned to the twice-daily dose regimen, the evening dose of investigational product will be administered 12 hours after the morning dose, and 2 hours prior to the evening meal. A snack or light meal may be provided to the subjects prior to the evening dose, provided it is consumed  $\geq 2$  hours prior to investigational product dose administration. It is suggested that lunch be divided into 2 portions, the first portion consumed at lunch, and the second portion consumed as the snack or light meal.

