During Treatments A, B and C, supplemental oral calcium and active vitamin D will be withheld starting on Day 1 (pre-dose), through the completion of all study procedures on Day 2 for both the once-daily and twice-daily dosing regimens. Upon completion of all study procedures on Day 2, subjects will then resume their usual supplemental oral calcium and active vitamin D at their next usual daily schedule.

During Treatments D, E and F, subjects will take their usual dose of supplemental oral calcium (but withhold active vitamin D) in the morning on Day 1, prior to investigational product administration. On Day 2, following the completion of all study procedures, subjects will then re-start their active vitamin D at their next usual daily schedule.

During the washout period, subjects will be instructed to take their usual doses of supplemental oral calcium and active vitamin D.

Any subject who experiences symptoms of hypocalcemia or hypercalcemia may be treated at the investigator's discretion, as per local standards. This may include, but is not limited to, intravenous (IV) calcium and/or fluids.

For all dosing regimens, rhPTH(1-84) will be administered in the morning of Day 1 of each treatment period following an overnight fast of at least 8 hours. Subjects will continue to fast

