### **4.5 Pharmacodynamic Set**

The Pharmacodynamic Analysis Set consists of all enrolled subjects who do not have major protocol violations that affect the validity of the PD results, receive at least 1 dose of rhPTH(1-84) and have at least 1 evaluable post-dose pharmacodynamic value available for 1 dose regimen. Subjects who do not meet the inclusion criterion for hypoparathyroidism will be excluded from the PD set. A listing of subjects excluded from the PD Set along with the reason for exclusion is to be generated. In the event of dosing error, proven or suspected based on PK data (extremely low post-dose PTH concentrations), PD data from the subject for the specific treatment period will be excluded. During treatments A, B, and C, if a subject takes supplemental oral calcium/active vitamin D within 24 hours post the last rhPTH(1-84) dose, PD data from the subject for the specific treatment period will be excluded from summary tables and figures. A listing of excluded PD data along with the reason for exclusion will be generated.

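### A schedule-table footnote lets Treatment A–C subjects restart calcium and vitamin D during BID sampling; SAP 4.5 then drops the whole period's PD data, including 0–24 h serum AUCs that a later intake cannot affect

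*SAP*

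**What the plan says.** **Body text.** For Treatments A, B and C, the Protocol Synopsis (Methodology) says that calcium and active vitamin D are "withheld starting on Day 1 (predose), through the completion of all study procedures on Day 2". Protocol 3.1 repeats this, "through the completion of all study procedures on Day 2 for both the once-daily and twice-daily dosing regimens", and adds for every cohort that "active vitamin D supplements must be withheld on Day 1 through completion of all study procedures on Day 2". SAP 2.1 agrees: "withheld starting on Day 1 (pre-dose), through the completion of all study procedures on Day 2".

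**Schedule table.** Protocol Table 1 has a row titled "Withhold supplemental oral calcium and active vitamin D", marked only on Day 1 of each period. Its footnote, which applies to Treatments A–C, ends the withholding with Day 1 and continues: "Subjects will then resume their usual supplemental oral calcium and active vitamin D at their next usual daily schedule on Day 2". It does not require that sampling be finished first. SAP Section 2.4, Table 2 (Schedule of Assessments), footnote t has the same wording. The rows for usual supplements and for calcium alone are also blank on Day 2, so the table does not settle the conflict.

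**Analysis rule.** SAP 4.5 acts, in Treatments A–C, "if a subject takes supplemental oral calcium/active vitamin D within 24 hours post the last rhPTH(1-84) dose, PD data from the subject" being the trigger. The consequence is that "PD data from the subject for the specific treatment period will be excluded from summary tables and figures". The excluded data are listed with the reason. Protocol 9.7 defines the pharmacodynamic population without this rule.

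**Parameters.** SAP 12.4.3 ends the serum AUC0-24h, AUCabove and AUCbelow at 24 h for both regimens; AUCnet is the difference of the last two. It gives no time limit for Emax, Emin or their times.

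**The concern.** Two live dosing instructions disagree, and the one in the schedule table is the one site staff may work from. A site that follows the footnote in a BID period (Treatment A or C) can give calcium or vitamin D while serum and urine sampling is still running. That has two effects.

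The late BID measurements no longer reflect the no-supplement condition. The intake also triggers SAP 4.5, which discards far more than it could have contaminated. Control of serum calcium and urinary calcium excretion is the primary objective. Treatments A and C are each given in one cohort, with at least 8 completers planned.

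**Working it through.** No test, power or precision figure is involved. The check is a timeline and a count.

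1. **Inputs.** The second BID dose is at 12 h (Protocol 3.1, SAP 2.1). The last BID time point is 36 h (Protocol Table 4, footnote k). There are 15 BID serum PD samples (Protocol Table 6), at predose, 1.5, 4, 6, 8, 10, 12, 13.5, 16, 18, 20, 22, 24, 28 and 36 h (SAP Table 4, BID regimen). There are 9 BID urine intervals: 0–3, 3–6, 6–9, 9–12, 12–15, 15–18, 18–24, 24–30 and 30–36 h (Protocol Table 4, footnote i).

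2. **Reproducing the plan's window.** The SAP 4.5 window ends 24 h after the last dose. BID: 12 + 24 = 36 h, which matches the last BID time point. QD: 0 + 24 = 24 h, which matches the last QD time point. SAP 4.5 and the body text therefore agree, and the footnote is the outlier.

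3. **Where the rule outruns the AUCs.** Window end minus AUC end is 36 − 24 = 12 h for BID and 24 − 24 = 0 h for QD. The mismatch exists only in BID periods.

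4. **Clock time (assumption: first dose between 07:00 and 10:00).** The 24-h point falls at 07:00–10:00 on Day 2. The 36-h point falls 12 h later, at 19:00–22:00. A usual midday supplement on Day 2, allowed by the footnote, is inside the window.

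5. **What an intake after the 24-h sample can reach.** Serum: 13 of 15 samples (13/15 = 86.7%) are at or before 24 h; only those at 28 and 36 h come later (15 − 13 = 2). Urine: 7 of 9 intervals (77.8%) end by 24 h; only 24–30 and 30–36 h come later (9 − 7 = 2). SAP 4.5 removes all 15 and all 9 from the summaries.

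6. **AUC check.** Illustrative serum calcium values on the BID grid were integrated by the linear trapezoid, the method SAP 12.4.3 names for AUCabove and AUCbelow. Then 0.3 was added to every value after 24 h. The 0–24 h area was unchanged (52.23 and 52.23). The 0–36 h area rose from 77.93 to 80.93, that is by 0.3 × 4/2 + 0.3 × 8 = 0.6 + 2.4 = 3.0. The values are invented; the invariance does not depend on them.

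7. **If Day −1 were removed as well.** Day −1 adds 9 serum samples (Protocol Table 6) and 7 urine intervals (Protocol Table 2). The unaffected share removed would be (13 + 9)/(15 + 9) = 22/24 = 91.7% of serum samples and (7 + 7)/(9 + 7) = 14/16 = 87.5% of urine intervals. This is a worst case that rests on one of two readings.

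**The case against.** The strongest reply is that the trigger may never occur. The body text forbids the intake in several places and names both regimens. Subjects stay in the research center until the last Day 2 assessment. Neither document gives a rate, and under the body text the planned loss is 0 of 8. That stands, so the percentages above describe one affected period and are not an expected loss.

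A second reply is that period-level exclusion is objective, prespecified and simple. It parallels the SAP's handling of dosing errors, and some BID outputs do run past 24 h. That stands as a reason to exclude the late measurements. It is no reason to exclude AUCs that were complete before the intake. The footnote also permits an intake early on Day 2, before the 24-h sample; that could affect the AUCs, and excluding them is then reasonable.

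Four stronger readings are tempting but not supported:

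- **Treatment A or C will be summarized on 7 subjects.** The Synopsis and Protocol 3.1 commit to enrolling enough subjects that at least 8 complete each treatment with sufficient data. Replacement and cohort expansion are the means. A final 7 would depart from the plan.
- **Day −1 is certainly lost.** SAP 12.4.3 and 12.4.5 place Day −1 within each treatment period and under the next day's treatment. The schedule tables label it as predose and prior to the treatment periods. The wording is ambiguous.
- **The 24-h urine totals are equally safe.** SAP 12.4.4 does not say which BID dose starts the 24 hours, so the claim is confined to the serum AUCs.
- **The BID versus QD comparison is biased.** SAP 12.4.5 specifies descriptive summaries by treatment and no paired contrast. No bias figure can be derived.

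**Conclusion.** The point holds, at minor to moderate severity. The footnote contradicts the body text in both documents. If it is followed in a BID period at 24–36 h, at most 2 serum samples and 2 urine intervals are compromised. SAP 4.5 then takes all 15 serum samples, all 9 urine intervals and four valid serum AUC measures per marker out of the summaries.

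The likely cost is one more subject to enrol or, if that is not done, avoidable loss of valid BID data: 1 of 8, or 12.5%, of that treatment per affected subject. The conclusion assumes that a site acts on the footnote and that the first intake follows the 24-h sample. The conflict and the counts are certain from the text; how often it would happen is unknown.

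**What to change.** 1. In Protocol Table 1 and SAP Table 2, change the footnote so that both supplements are withheld until every Day 2 procedure is finished, and mark the withholding row on Day 2 of both periods. This removes the cause.

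2. In SAP 4.5, for a first intake after the 24-h sample, keep AUC0-24h, AUCabove, AUCbelow and AUCnet, all serum samples and urine intervals completed before the intake, and Day −1. Exclude only later samples and the intervals that end after the intake. This protects valid data if the footnote has already been followed.

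3. Do not cut Emax, TEmax, Emin and TEmin to 0–24 h for everyone, because that would discard 24–36 h information from unaffected BID subjects. For an affected subject, leave these four out of the summaries or derive them from pre-intake samples with a flag.

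Optional clarifications: name the dose that starts the BID 24-h urine totals in SAP 12.4.4, and say whether calcium given for symptoms counts as intake under SAP 4.5.

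Cost: one footnote and one table row in each document, and a few sentences in SAP 4.5. No new data are needed, because Protocol 5.2 already requires supplement times and doses in the CRF for Days −1, 1 and 2. The price is that n varies by time point when a subject is affected.

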## **5. SUBJECT DISPOSITION**

A listing of all Screen Failures (ie, subjects who were screened but not randomized) will be presented along with reasons for screen fail and details of any AEs. Final subject numbers will be presented for subjects that had been re-screened.

The number of subjects included in each subject population set (ie, Screened, All-Enrolled, Safety, Pharmacokinetic, and Pharmacodynamic) will be summarized by treatment sequence, and by treatment.

For the summary by treatment sequence, the numbers and percentages of subjects who either completed or prematurely discontinued during the study will be presented for each treatment sequence and overall for the Safety Analysis Set. Reasons for premature discontinuation from the study as recorded on the termination page of the eCRF will be summarized (number and percentage) for each period (Period 1, Washout, Period 2, and Follow-up) by treatment sequence and overall for the Safety Analysis Set.

A similar summary table will be presented for the summary by treatment, with number and percentage of subjects who discontinued during that treatment period for the Safety Analysis Set.

All subjects who prematurely discontinued during the study period will be listed by discontinuation reason for the All-Enrolled Set.

## **6. PROTOCOL DEVIATIONS**

A summary of the number and percentage of subjects in the All-Enrolled Set with protocol violations or deviations will be produced.

All protocol violation and deviation data will be listed for the All-Enrolled Set.

## 7. DEMOGRAPHIC AND OTHER BASELINE CHARACTERISTICS

Descriptive summaries of demographic and baseline characteristics will be presented by treatment sequence and overall for the Safety Analysis Set.

The following demographic characteristics will be summarized in the following order in the tables: age, sex, ethnicity, race, weight, height, BMI, and BMI category (Underweight [ $<18.5 \text{ kg/m}^2$ ], Normal [ $18.5$  to  $24.99 \text{ kg/m}^2$ ], Overweight [ $25.0$  to  $29.99 \text{ kg/m}^2$ ], Obese [ $\geq 30.0 \text{ kg/m}^2$ ], Missing). In addition, other baseline characteristics will be summarized.

Height and weight at screening will be used to calculate BMI using the formula below:

$$\text{BMI} = \frac{\text{weight [kg]}}{(\text{height [m]})^2}$$

A listing will be created to show all the demographics and baseline characteristics for each enrolled subject.

A table for Parathyroid History will summarize the last record of active vitamin D or calcium supplementation prior to study medication. The dose of active vitamin D will be categorized as low ( $0-0.25 \text{ }\mu\text{g/day}$ ), medium ( $>0.25-0.5 \text{ }\mu\text{g/day}$ ) or high ( $>0.5 \text{ }\mu\text{g/day}$ ), and the dose of calcium supplementation will be categorized as  $0-2000 \text{ mg/day}$  or  $>2000 \text{ mg/day}$ . The number and percentage of subjects in each category will be presented. Duration of hypoparathyroidism will be calculated from the date of informed consent and onset of hypoparathyroidism obtained from the medical history page. This will be summarized using standard summary statistics and also by number and percent of subjects in the categories  $\leq 5$  years,  $>5-10$  years, and  $>10$  years.

Medical history will be coded using MedDRA version 19.0 or newer, and summarized by system organ class (SOC), preferred term (PT), and treatment sequence. Medical history will be listed for the Safety Analysis Set.

